## **CLINICAL PARAMETERS**

For each measurement of vital signs (*i.e., systolic and diastolic blood pressures*), weight, pulse rate and SpO2 split by conditions of measurement (*either on room air or on oxygen*), quantitative descriptive statistics will be tabulated by study group (*and globally*) and visit, using the observed case approach.

For each parameter separately (*i.e., systolic and diastolic blood pressures, weight, pulse rate and SpO2 on room air*), the absolute variations "*post-Run-In Period – baseline (measured at Selection)*" will also be tabulated by study group (*and globally*) and visit throughout the *Follow-Up Period*.

In the subgroup of patients on oxygen therapy at Selection for whom pulse rate and/or SpO2 are measured at least once on oxygen from Visit 1 onwards, the absolute variations "*post-Run-In Period – baseline (measured at Selection)*" on oxygen will also be tabulated by study group (*and globally*) and visit throughout the *Follow-Up Period* for all collected measurements on oxygen.

Moreover, to visualise the evolution of the data collected separately, arithmetic means of each parameter (*i.e., systolic and diastolic blood pressures, weight, pulse rate and SpO2 on room air*) and their 95.0% confidence intervals will be represented graphically (*the x-axis being the assessment time-axis and the y-axis being the arithmetic mean-axis*) with both study groups being represented separately on the same graph, using the observed case approach.

## **CHARLSON COMORBIDITY INDEX**

The Charlson Comorbidity Index scores recorded by the investigators will be summarised descriptively by study group (*and globally*) and visit, using the following statistics: number of patients, mean, standard deviation, minimum, median and maximum raw values. The absolute variations "*post-Run-In Period – baseline (evaluated at Visit 1)*" will also be tabulated by study group (*and globally*) and visit throughout the *Follow-Up Period*.

## **ARTERIAL OR CAPILLARY BLOOD GASES**

For each arterial blood gas assayed (*i.e.*, pH, PaO2, PaCO2, HCO3, HbCO and SaO2), separately, quantitative descriptive statistics of recorded values will be tabulated by study group (*and globally*) and visit, using the observed case approach.

Moreover, to visualise the evolution of each arterial blood gas assayed, arithmetic means of the recorded values of pH, PaO2, PaCO2, HCO3, HbCO and SaO2, separately and their 95.0% confidence intervals will be represented graphically (*the x-axis being the assessment time-axis and the y-axis being the arithmetic mean-axis*) with both study groups being represented separately on the same graph, using the observed case approach.

## **HAEMOGLOBIN, HAEMATOCRIT AND C-REACTIVE PROTEIN (CRP)**

For haematology and CRP results, separately, the following descriptive statistics will be tabulated by study group (*and globally*) and visit, using the observed case approach:

- number of patients, mean, standard deviation, minimum, median and maximum raw values (*converted in international units, if necessary*),
- number and percentage of patients above, below or within normal ranges in use in each laboratory involved.

The absolute variations "*post-Run-In Period – baseline (measured prior to Visit 1)*" will also be tabulated by study group (*and globally*) and visit throughout the *Follow-Up Period*.

A shift table will also be provided for haemoglobin, haematocrit and CRP separately to depict the number and percentage of patients with *post-Run-In Period* decreased laboratory values (*from Within Normal Ranges to Below, from Above normal ranges to Within Normal Ranges or from Above normal ranges to Below*), the number and percentage of patients without changes (*either always Within Normal Ranges or Above or Below*) and the number and percentage of patients with *post-Run-In Period* increased laboratory values (*from Below to Within Normal Ranges, from Within Normal Ranges to Above or from Below normal ranges to Above*) by study group (*and globally*), as compared to their baseline values (*measured prior to Visit 1*).

Moreover, the number and percentage of patients with *post-Run-In Period* anaemia or polycythemia (*as defined in section 6.B.2*) at each visit separately will be tabulated by study group (*and globally*).

## **DESCRIPTION OF CONCOMITANT TREATMENTS**

All concomitant treatments with start date at the earliest on the day of the patient's randomisation will be tabulated descriptively by study group (*and globally*), on the ITT data set (*defined in section 7.B.3.1*), using the WHO-DRUG dictionary and the Anatomical Therapeutic Chemical (ATC) classification. All reported concomitant treatments will be classified in two (2) successive periods: the *Run-In Period* and the *Follow-Up Period*, according to their start date.

Over these two (2) periods, separately and globally, three (3) summary tables will be provided by study group (*and globally*):

- one table showing the number and percentage of patients with at least one concomitant treatment with start date at the earliest on the day of the patient's randomisation, by therapeutic area (*ATC1 code corresponding to ATC system main group*),
- one table by both ATC1 code and ATC system subgroup (*ATC2 code*),
- and one table showing the number and percentage of patients with at least one respiratory system concomitant treatment with start date at the earliest on the day of the patient's randomisation, by ATC system subgroups (*ATC2, ATC3 and ATC4 codes*).

Additionally, over the *Run-In Period* and the *Follow-Up Period*, separately and globally the number and percentage of patients for whom either Continuous Positive Airway Pressure (CPAP) or home Non-Invasive Ventilation (NIV) separately is implemented (*while the patient was free of both of them at Selection*) will be tabulated descriptively by study group (*and globally*), on the ITT data set, with their average daily duration prescribed.

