## 5.D CONCOMITANT TREATMENTS

All concomitant treatments administered to the patient (*including vaccines, oxygen therapy, home ventilation and CPAP*) will be recorded by the investigators in the e-CRF, with the following information:

- **For the pharmaceutical therapies:** treatment names and dosage, route of administration, dose per administration and posology, start and end dates or ongoing medication, and the reason for their prescription,
- **For the vaccines:** names and date of administration,
- **For oxygen therapy:** start and, if applicable, end dates, daily prescribed hours of use, prescribed flow rates (*at rest, during exercise and during sleep*), type of oxygen source(s) including the name of the device(s) used,
- **For home ventilation and CPAP:** start and end dates, if applicable.

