Results of the most recent pulmonary function tests performed in stable state prior to Selection, and results of the pulmonary function tests performed during the *Run-In Period* will be tabulated descriptively (*as both raw values and percentages of predicted values, when applicable*), by study group (*and globally*), together with the ratios FEV1/FVC and RV/TLC (*in the subgroup of patients for whom body plethysmography measurements at Visit 1 were collected*) as reported by the investigators in the electronic Case Report Forms.

No systematic statistical test will be performed to compare both groups of patients at Selection and during the *Run-In Period (up to the end of Visit 1)* on any data sets analysed. They will only be performed if any clinically significant imbalances between study groups appear to be of major importance for the interpretation of the primary efficacy criterion results and need to be cautiously examined in order to determine whether the randomisation has failed or not. If this descriptive analysis provides any clues on potential imbalances, further statistical investigations will be carried out using homogeneity tests and if necessary, the factor adjusting strategy will be redefined and the corresponding potentially predictive factor will be added to the ones pre-listed in section 7.B.3.5.

Concomitant diseases, as well as medical and surgical histories will be tabulated descriptively by study group (*and globally*) using the MedDRA codes of System Organ Classes and preferred terms.

All concomitant treatments with start date at the latest on the day preceding the patient's randomisation will be tabulated descriptively by study group (*and globally*) using the WHO-DRUG dictionary and the Anatomical Therapeutic Chemical (ATC) classification. Three (3) tables will be provided:

- one table showing the number and percentage of patients with at least one concomitant treatment with start date at the latest on the day preceding randomisation, by therapeutic area (*ATC1 code corresponding to ATC system main group*),
- one table by both ATC1 code and ATC system subgroup (*ATC2 code*),
- and one table showing the number and percentage of patients with at least one respiratory system concomitant treatment with start date at the latest on the day preceding randomisation, by ATC system subgroups (*ATC2, ATC3 and ATC4 codes*).

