## **EXTENT OF EXPOSURE**

Duration of the *Run-In Period*, duration of the *Follow-Up Period* and overall study duration will be tabulated (*expressed in months, rounded at one digit*) by study group (*and globally*), as both quantitative and categorical data.

Overall study duration is defined as the time interval between the actual date of Selection (*included*) and the actual date of the last visit (*or phone contact*) performed by the investigator (*visit planned to be performed at the time of premature withdrawal or on theoretical visit date corresponding to Month 24 (for the first patients included in the study) or Month 12 (for the patients included afterwards)*) (*excluded*), *i.e., as the quantity “date of last visit performed by the investigator - date of Selection”*.

Cumulative individual number of days on oxygen therapy will be tabulated (*expressed in months, rounded at one digit*) by study group (*and globally*), as both quantitative and categorical data. It will be calculated taking into account the individual start date of each oxygen prescription and its corresponding end date, if applicable, for each oxygen prescription overlapping the overall study duration previously defined. If a given patient starts his/her oxygen therapy after his/her date of Selection in the study and if he/she ends it definitively before his/her last study visit, his/her individual number of days on oxygen therapy will be calculated as “end date of the oxygen prescription – start date of the oxygen prescription + 1 day”. For patients who were never prescribed oxygen therapy throughout their whole study participation, the individual number of days on oxygen therapy will be described as equal to 0 days.

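### The on-study medication tables count new starts, not treatment received, so the Follow-Up columns cannot describe drug co-treatment by arm

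*Protocol*

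**What the plan says.** Four places in the protocol bear on this.

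- **Section 7.B.3.7, Description of concomitant treatments.** The on-study tables take "All concomitant treatments with start date at the earliest on the day of the patient's randomisation". Then "All reported concomitant treatments will be classified in two (2) successive periods", Run-In and Follow-Up, "according to their start date". On display: "Over these two (2) periods, separately and globally, three (3) summary tables will be provided by study group". Nothing carries a continuing treatment from one period to the next. A further sentence counts newly implemented CPAP and NIV separately, but only in patients who had neither at Selection.
- **Section 7.B.3.2.** The mirror-image baseline set: "All concomitant treatments with start date at the latest on the day preceding the patient's randomisation will be tabulated descriptively by study group", at the same ATC levels.
- **Section 5.D.** For drugs the e-CRF records "start and end dates or ongoing medication". For home ventilation and CPAP it records start and end dates.
- **Section 7.B.3.7, Extent of exposure.** Days on oxygen are counted differently, "for each oxygen prescription overlapping the overall study duration previously defined".

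**The concern.** A table of concomitant treatments by study period is normally read as what patients were taking in that period. Here the Follow-Up columns hold only what was begun in that period. Most maintenance treatment in patients with GOLD III/IV COPD is likely to predate randomisation, so the columns leave out much of the drug treatment actually received.

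This matters because the trial is open, medication is at the investigator's discretion (Section 5.D.1), and the working hypotheses expect better compliance and earlier treatment (Section 1.C). A reader who wants to describe how co-treatment differed between arms during Follow-Up, when the primary criterion accrues, will turn to these tables and not find it. If the arms differ in when drugs are started, or in use before randomisation, the columns could also suggest a difference in use that is not there.

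The ventilation count has a related gap: a CPAP user who is given NIV during the study, or the reverse, is excluded from the new-start count.

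**Working it through.** The protocol gives no figure on concomitant treatment, so there is none to reproduce. The check follows a treatment through the rule and then illustrates the size with assumed percentages.

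**Where a treatment appears**

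| Treatment | Baseline table (7.B.3.2) | Run-In | Follow-Up | Combined |
|---|---|---|---|---|
| Begun before randomisation, continued all year | yes | no | no | no |
| Begun in Run-In, continued all year | no | yes | no | yes |
| Begun in Follow-Up | no | no | yes | yes |

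Only the third row reaches the Follow-Up column. The baseline table does not show whether a treatment in the first row continued.

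**Size, on assumed figures**

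For one drug class, let b be the percentage of patients already on it before randomisation, r the percentage starting it in Run-In and f the percentage starting it in Follow-Up. Assume each patient starts once and continues. Then:

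- true use in Follow-Up = b + r + f
- planned Follow-Up column = f
- planned combined column = r + f

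In each cell below, Intervention comes first and Control second.

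| b | r | f | True use | Follow-Up column | Difference (points) | Combined column |
|---|---|---|---|---|---|---|
| 60 / 60 | 20 / 5 | 5 / 20 | 85 / 85 | 5 / 20 | −15 | 25 / 25 |
| 60 / 60 | 10 / 5 | 10 / 15 | 80 / 80 | 10 / 15 | −5 | 20 / 20 |
| 85 / 85 | 5 / 2 | 5 / 8 | 95 / 95 | 5 / 8 | −3 | 10 / 10 |
| 70 / 70 | 10 / 10 | 10 / 10 | 90 / 90 | 10 / 10 | 0 | 20 / 20 |

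With the planned 153 patients per group (Section 7.B.2) as an approximate denominator, the first row is 0.05 × 153 ≈ 8 against 0.20 × 153 ≈ 31 patients. All four rows have equal true use, and the combined column is equal in all four.

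**What the combined table does not repair**

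Let prior use be 60% against 70%, and true use in Follow-Up 80% in both arms. The combined column then shows 80 − 60 = 20% against 80 − 70 = 10%. Equal use appears as a 10-point difference, because treatment begun before randomisation is excluded from every on-study table.

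**Ventilation**

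A patient on CPAP at Selection who starts NIV in Follow-Up fails the condition of having neither at Selection. The patient is therefore missing from the new-NIV count, although NIV and CPAP are to be reported separately.

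**The case against.** The strongest reply is that this is an ordinary split between prior treatment and new starts, and the plan says so. Two of the three on-study table descriptions repeat the start-date condition, and the baseline set covers the same ATC levels. A maintenance inhaler taken by 90% of both arms since before randomisation would show as 90% against 90% at baseline and 0% against 0% in Follow-Up, with no false difference. Where only start timing differs, the Run-In and combined tables beside the Follow-Up column reveal it. Oxygen is already counted by overlap, and new oxygen starts have their own description in Section 7.B.3.5. All of this stands, and it limits the point to descriptive tables. It does not supply a table of drugs received during Follow-Up.

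A reader might infer three stronger things that the documents do not support.

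- **That the programme shifts prescribing into Run-In in the Intervention group.** Only that group has the four home sessions, but the counsellor's reports in Section 4.B.3.1 concern understanding and skills. The route to a therapeutic adjustment runs through confirmed alarms in the telephone follow-up (Appendix 2), which belongs to the Follow-Up Period. A difference in start timing is possible but is an assumption here.
- **That medication is a rival explanation for the primary result.** Drug changes caused by allocation come after randomisation and are part of how the strategy works. They may describe mechanism; they do not confound the randomised comparison.
- **That a CPAP user who starts NIV is lost to every analysis.** The exploratory regression in Section 7.B.3.5 includes need for oxygen and/or NIV at Selection and/or during the study. The gap is in the new-start count only.

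**Conclusion.** The point holds and is minor. The start-date rule is stated in the protocol, not left open. Under it, the tables headed as the description of concomitant treatments show new starts, and no planned drug table shows treatment received by arm in Follow-Up.

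The columns could mislead only if the arms differ in start timing or in prior use and the table is read as use. With equal true use, the assumed scenarios give a Follow-Up difference of 0 to 15 points, and 0 when start timing and prior use are the same in both arms. The percentages are illustrative and assume that each treatment, once started, continues.

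Section 7.B.3.7 applies no test to these data, and the primary analysis does not use them.

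**What to change.** 1. Count a treatment in every period that its start-to-end interval overlaps, treating an ongoing entry as running to the patient's last study contact. Drugs begun before randomisation or in Run-In and still taken then appear under Follow-Up. This follows the overlap rule the protocol already uses for oxygen.
2. Keep the present tables, and title them as treatments newly started since randomisation.
3. Count new NIV among patients not on NIV at Selection, and new CPAP among patients not on CPAP at Selection, so that a CPAP user who starts NIV (or the reverse) is included.

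The cost is a change of wording, a few extra tables and some programming. Section 5.D already collects the dates and ongoing status, so no new data are needed.

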## 8. ADVERSE EVENTS

---

### 8.A DEFINITION

An adverse event is defined as any undesirable and unintended sign or symptom (*that could include a clinically significant abnormal laboratory finding*) occurring in a patient participating to a clinical trial and which does not necessarily have a causal relationship with the study intervention.

Adverse events are classified by the investigator according to their severity (*mild, moderate or severe*).

A **Serious Adverse Event (SAE)** is any adverse event which:

- Results in death\*,
- Is life-threatening (*actually places the patient at risk of death at the time of the event*),
- Requires patient hospitalisation or prolongation of existing hospitalisation,
- Results in disability or incapacity (*e.g., any temporary or permanent clinically significant handicap*),
- Is a congenital anomaly/birth defect,
- Or is considered serious by the investigator.

\* Death is an outcome and usually not the reported term of the SAE. For example, if “*death due to myocardial infarction*” occurs, myocardial infarction should be reported as the SAE and death should be reported as its outcome.

All adverse events not corresponding to these definitions will be considered not serious Adverse Events (**AEs**).

### 8.B COLLECTION AND REPORTING OF SERIOUS ADVERSE EVENTS

The investigator is responsible for the detection and documentation of events meeting the definition of an AE or SAE as provided in this protocol. In order to fulfil the safety reporting obligations, the investigator should report all Serious Adverse Events occurring during the study, whether related to the study intervention or not, within 24 hours in the dedicated screen of the e-CRF, or when the e-CRF is not available, by fax or telephone to ITEC Services, for the attention of:

1. [name] [name], ITEC Services
2. [name], ITEC Services
3. [name], ITEC Services

[contact]

[contact]

A copy of the document to be filled in and faxed in case the e-CRF is not available will be provided in the investigator binder.

If ITEC Services cannot be reached, AIR LIQUIDE *Santé* INTERNATIONAL Pharmacovigilance department should be contacted:

Tel: [name]  
[contact]  
Email : [contact]

If the Pharmacovigilance Department cannot be reached, AIR LIQUIDE *Santé* INTERNATIONAL COMET study team at the Research and Development Centre Claude Delorme could be contacted:

Tel: [name]  
[contact]

The initial SAE declaration should include the following information: patient selection number, brief description of the event, its start date, and the reason(s) why the investigator considers the event serious.

The time period for the consideration and reporting of AEs (*either serious or not, according to their regulatory definition provided in section 8.A*) starts at the patient Selection (*i.e., at Visit 0*) and continues up to the last study visit (*i.e., up to Visit 5*).

The medical devices provided by AIR LIQUIDE *Santé* INTERNATIONAL for the study conduct are all CE marked and they are not under evaluation during the study. The investigators should thus follow the regular process for reporting any incidents and near-incidents related to those medical devices, whenever they occur throughout the study period.

## 9. ADMINISTRATIVE AND REGULATORY ASPECTS

---

### 9.A ETHICS COMMITTEES AND NATIONAL COMPETENT AUTHORITIES

The study will be conducted in compliance with Good Clinical Practice guidelines, the most recent revised version of the Declaration of Helsinki (*Seoul, October 2008 attached in Appendix 1*) and the European Directive 2001/20/EC on 4th April 2001 (*on the approximation of the laws, regulations and administrative provisions of the Member States relating to the implementation of good clinical practice in the conduct of clinical trials on medicinal products for human use*).

The protocol and subsequent substantial amendments (*if applicable, see section 9.D*) are to be submitted to the local ethics committee and national competent authority for approvals in each participating country.

The enrolment of patients in the study could be started in a given participating country only after the written approvals of the corresponding local ethics committee and national competent authority.

### 9.B PATIENT INFORMATION AND CONSENT

The investigator must provide the patient with a verbal explanation of the study in which the patient is invited to take part, particularly, concerning the study intervention, the expected benefits and potential risks faced during the study. The investigator must also answer any questions the patient may have regarding the study. The patient must be given an information sheet which is easy to understand in their native language. A blank copy of the patient information sheet in each local study language will be submitted to the ethics committees for approvals, together with the protocol.

**Informed Consents forms signed by the patient** prior to his/her study participation will be provided in three (3) copies:

- One signed copy to be given to the patient,
- One signed copy to be kept by the investigator,
- One signed copy to be placed by the investigator in an envelope for the sponsor. This envelope will be sealed with the CRA during one monitoring visit (*see section 9.C*).

